4.8 Repeat Dose Administration study (Stage 2)

Primary objective

To evaluate the safety of repeat dose administrations of fresolimumab in adults with moderate-to-severe OI with respect to:

- Vital signs - heart rate, blood pressure, respiratory rate, and body temperature.
- Laboratory variables.
- EKG.
- Adverse events and serious adverse events.

Secondary Objectives

Effect of fresolimumab with respect to:

- Markers of bone turnover in blood (type 1 procollagen, N-terminal or P1NP, Osteocalcin or Ocn, and C-terminal telopeptide or CTX).
- Areal bone mineral density (aBMD) at the hip or the lumbar spine as measured by dual-energy X-ray absorptiometry (DXA) scan.
- Bone density and estimated strength by pQCT of forearm.
- Pain score as assessed by Numeric Rating Scale (NRS).

- Forced expiratory volume in 1 second (FEV1), forced vital capacity (FVC) as measured by pulmonary function tests
- QOL as assessed by PROMIS®.
- Functional capacity as assessed by the 6-minute walk test.

Dose

Group 1

- 4 subjects receive four intravenous infusions of fresolimumab- months 0, 3, 6, and 9, with a follow up period of 3 months (total duration of study participation 12 months).

Group 2

- 4 subjects receive two intravenous infusions of fresolimumab- months 0 and 6, with a follow up period of 6 months (total duration of study participation 12 months).

The dose regimen has been selected based on the duration of bone remodeling cycle that can vary from 3-6 months. The dose regimen and duration are similar to studies that have been conducted with denosumab (Prolia ®), a monoclonal antibody that inhibits receptor activator of nuclear factor kappa-B ligand (RANKL), which has been approved for the treatment of osteoporosis.²⁴ Repeat doses of both 1 mg/kg and 4 mg/kg body weight of fresolimumab, have been studied in a trial titled “A Phase 2, Multicenter, Double-Blind, Parallel Dosing, Randomized Study of Fresolimumab or Placebo in Patients with Steroid-Resistant Primary Focal Segmental Glomerulosclerosis” under IND 100054. This study had four monthly IV administrations of fresolimumab at either 1 mg/kg or 4 mg/kg or placebo with treatment duration of 12 weeks and observation duration of 24 weeks after last dose of study medication. The dose and the number of doses being proposed for our study are similar but far less frequent than used in the study under IND 100054.

Study Procedures

This study will require up to eight visits at a participating clinical site of the BBD consortium. Laboratory tests, ECGs, and radiographs obtained during this study will be interpreted locally by the PIs.

A patient can be enrolled in the study only after an in-person screening visit which will be conducted at BCM. Day 1 visit, during which the participant will receive the study medication will have to be an in-person visit at BCM. Participants are expected to come in for the follow up visits to the study site at BCM. However if there are unforeseen circumstances, or safety reasons (e.g., COVID-19) due to which a participant is unable to travel to BCM, for the follow up visits, an attempt will be made to accommodate study procedures virtually and/or at a remote site which is close to the place of the residence.

Screening visit procedures

- Obtain informed consent.
- Record medical history.
- Determine if participant has used or is using an exclusionary medication.
- Determine if participant plans to have invasive dental work or skeletal surgery during the period of the study
- Perform physical examination.

- Measure vital signs - heart rate, blood pressure, respiratory rate, and body temperature.
- Measure height, weight, arm span.
- Collect blood sample for laboratory tests (Safety: comprehensive metabolic panel (CMP), complete blood count (CBC), PT/INR, vitamin D testing, bone remodeling markers [serum C-terminal telopeptide of type 1 collagen (CTX), Osteocalcin (Ocn), and amino-terminal propeptide of type I collagen, P1NP)], and lymphoblast culture for gene expression studies).
- Confirm that the subject has a genetic test demonstrating that s/he has a Glycine substitution in *COL1A1* or *COL1A2*, or pathogenic variants in *CRTAP*, *PPIB*, or *LEPRE1*. If not present, collect sample for DNA testing.
- Collect urine sample for laboratory test (Safety: urinalysis OR urine dipstick, urine pregnancy test for women of child-bearing age).
- Perform skeletal survey (if historical x-rays are not available to review and ascertain the bony deformities or scoliosis).
- Perform a 12-lead EKG.
- Perform tuberculosis screening by a positive purified protein derivative (PPD) test or Interferon-gamma release assay.

Prior to enrollment (Day 1) screening eligibility criteria for each subject will be reviewed by participating investigators. Individuals who meet the criteria for enrollment will have Study Visit 1 within 60 days of screening.

Day 1 visit procedures (Baseline)

- Review and confirm that the subject meets all criteria for inclusion.
- Confirm that the subject would not be excluded based on screening laboratory tests, a clinically significant infection, a recent fracture or use of any medications since the screening visit that would exclude them from participation.
- Measure vital signs - heart rate, blood pressure, respiratory rate, and body temperature.
- Collect urine from female subjects to determine pregnancy status.
- Perform DXA scan of the lumbar spine (test may not be performed if there is significant scoliosis or the patient has had spinal instrumentation).
- Perform DXA scan total hip and femoral neck (test may not be performed if there are pins or rods in the region of interest).
- Perform a peripheral quantitative CT (pQCT) of the forearm.
- Perform a pulmonary function test.
- Perform a 6-minute walk test.
- Collect Numeric Rating Scale (NRS) and PROMIS® 29 questionnaire responses.
- Collect blood for immunogenicity (measure antibodies against fresolimumab) and for pharmacokinetics prior to infusion of fresolimumab.
- Intravenous infusion of fresolimumab over 30 minutes.
- Collect blood for pharmacokinetics after the end of the infusion.
- Subjects will be monitored for three hours for any infusion-related

reactions (document adverse events) and will be discharged home.

Day 15 visit procedures

- Perform a physical exam.
- Measure vital signs - heart rate, blood pressure, respiratory rate, and body temperature.
- Perform a 12-lead EKG.
- Collect blood for laboratory tests (Pharmacokinetics; Immunogenicity; Lymphoblast culture).
- Document adverse events include bleeding assessment.

Day 30 visit procedures

- Perform a physical exam.
- Measure vital signs - heart rate, blood pressure, respiratory rate, and body temperature.
- Collect blood for laboratory tests (Safety: CBC, CMP, PT/INR; Pharmacokinetics; Bone remodeling markers; Immunogenicity; Lymphoblast culture).
- Collect urine sample for safety test (urinalysis OR urine dipstick).
- Record adverse events assessment including history of any oral or mucosal bleeding.

Day 90 visit procedures

- Perform a physical exam.
- Measure vital signs - heart rate, blood pressure, respiratory rate, and body temperature.
- Collect NRS responses.
- Collect blood for laboratory tests (Safety: CBC, CMP, PT/INR; Pharmacokinetics; Bone remodeling markers; Immunogenicity; Lymphoblast culture).
- Collect urine sample for laboratory test (Safety: urinalysis OR urine dipstick, urine pregnancy test for women of child-bearing age).
- Perform a 12-lead EKG.
- The cohort of subjects randomized to receive four infusions of study drug will receive second dose of fresolimumab. The cohort of subjects randomized to receive two infusions of study drug will not receive any drug during this visit.
- Intravenous infusion of fresolimumab over 30 minutes.
- Collect blood for pharmacokinetics after the end of the infusion.
- Document adverse events.

Day 180 visit procedures

- Perform a physical exam.
- Measure vital signs - heart rate, blood pressure, respiratory rate, and body temperature.
- Collect NRS and PROMIS® 29 responses.
- Collect blood for laboratory tests (Safety: CBC, CMP, PT/INR;

- Pharmacokinetics Bone remodeling markers; Immunogenicity
- Collect urine sample for laboratory test (Safety: urinalysis OR urine dipstick, urine pregnancy test for women of child-bearing age.)
- The cohort of subjects randomized to receive four infusions of study drug will receive the third dose of fresolimumab. The cohort of subjects randomized to receive two infusions of study drug will receive the second.
- Intravenous Infusion of fresolimumab over 30 minutes.
- Collect blood for pharmacokinetics after the end of the infusion.
- Document adverse events

Day 270 visit procedures

- Perform a physical exam.
- Measure Vital signs - heart rate, blood pressure, respiratory rate, and body temperature.
- Collect NRS responses.
- Collect blood for laboratory tests (Pharmacokinetics; Bone remodeling markers).
- Collect urine for urine pregnancy test in women.
- The cohort of subjects randomized to receive four infusions of study drug will receive fourth dose of fresolimumab. The cohort of subjects randomized to receive two infusions of study drug will not receive any drug during this visit.
- Intravenous Infusion of fresolimumab over 30 minutes.
- Collect blood for pharmacokinetics after the end of the infusion.
- Document adverse events.

Day 360 visit procedures

- Perform a physical exam
- Measure Vital signs - heart rate, blood pressure, respiratory rate, and body temperature (including height, weight, arm span)
- Collect NRS and PROMIS® 29 responses
- Collect blood for laboratory tests (Safety: CBC, CMP, PT/INR; Pharmacokinetics; Bone remodeling markers; Immunogenicity; Lymphoblast culture)
- Collect urine sample for laboratory test (Safety: urinalysis OR urine dipstick, urine pregnancy test for women of child-bearing age.)
- Perform a 12-lead EKG
- Perform DXA scan of the lumbar spine (test may not be performed if there is significant scoliosis or the patient has had spinal instrumentation)
- Perform DXA scan total hip and femoral neck (test may not be performed if there are pins or rods in the region of interest)
- Perform a peripheral QCT
- Perform a pulmonary function test
- Perform a 6-minute walk test
- Document adverse events.

- Subjects' participation will conclude when they are discharged home following this visit.

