- Collect blood for pharmacokinetics after the end of the infusion.
- Subjects will be monitored for three hours for any infusion-related reactions (document adverse events) and will be discharged home.

Day 15 visit procedures

- Perform a physical exam.
- Measure vital signs - heart rate, blood pressure, respiratory rate, and body temperature.
- Record adverse events assessment including history of any oral or mucosal bleeding.
- Perform a 12-lead EKG.
- Collect blood for laboratory tests (Safety: CBC, CMP, PT/INR; Pharmacokinetics; Lymphoblast culture).
- Collect urine sample for laboratory test (Safety: urinalysis OR urine dipstick).
- Document adverse events.

Day 30 visit procedures

- Perform a physical exam.
- Measure vital signs - heart rate, blood pressure, respiratory rate, and body temperature.
- Collect blood for laboratory tests (Safety: CBC, CMP, PT/INR; Pharmacokinetics; Bone remodeling markers).
- Collect urine sample for laboratory test (Safety: urinalysis OR urine dipstick).
- Record adverse events assessment including history of any oral or

mucosal bleeding.

Day 90 visit procedures

- Perform a physical exam.
- Measure vital signs - heart rate, blood pressure, respiratory rate, and body temperature.
- Record medical history.
- Collect blood for laboratory tests (Safety: CBC, CMP, PT/INR; Pharmacokinetics; Bone remodeling markers).
- Collect urine sample for laboratory test (Safety: urinalysis OR urine dipstick).
- Document adverse events.

Day 180 visit procedures

- Perform a physical exam.
- Measure vital signs - heart rate, blood pressure, respiratory rate, and body temperature.
- Record adverse events.
- Collect blood for laboratory tests (Safety: CBC, CMP, PT/INR; Pharmacokinetics; Bone remodeling markers).
- Collect urine sample for laboratory test (Safety: urinalysis OR urine dipstick)
- Perform a 12-lead EKG.
- Perform DXA scan of the lumbar spine (test may not be performed if there is significant scoliosis or the patient has had spinal instrumentation).
- Perform DXA scan total hip and femoral neck (test may not be performed if there are pins or rods in the region of interest).
- Document adverse events.

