4.9 Data Elements

Once referred for screening, the participant's diagnostic testing will be reviewed to assure that the correct OI classification has been made and eligibility requirements are met based on study inclusion and exclusion criteria. Data will be collected at study visits per the **Schedule of Events for each study group**. We will use a variety of methods to obtain these data. Certain information will be obtained from a historical review of existing charts and laboratory/treatment data. Other data will be obtained from patients or their families through a standard interview, examination or laboratory/functional testing. The investigators who will perform functional assessments and other critical evaluations will be included as investigators on their local institution's IRB application.

Medical History: Medical history will be recorded on a history and physical examination form.

12-lead EKG: EKG at the screening visit then at 2 subsequent study visits for all study participants.

Bone mineral density: A dual-energy x-ray absorptiometry (DXA) at the lumbar spine, total hip and femoral neck will be performed.

X-rays of the spine: Standard posterio-anterior and lateral views will be taken, preferably in the standing position. If this is not possible, these radiographs will be obtained in the sitting position. If participants not able to sit, the X-rays will be taken in the supine position. Taking each of the two views on a single film (skull base to sacrum) is preferred. All radiographic images will be reviewed at the screening visit to determine eligibility. Historical surveys are acceptable if X-rays taken demonstrate the boney abnormalities that are required as inclusion criteria.

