4.10 Schedule of Events

Procedures	Screening	Treatment				
		1	15	30	90	180
	-60 d window	±3 d window		±7 d window		
Informed Consent	X					
Medical History	X					
Physical Examination	X		X	X	X	X
Vital signs - heart rate, blood pressure, respiratory rate, and body temperature	X	X	X	X	X	X
Height	X					
Weight	X					
Blood/Urine for Safety labs (CBC, CMP, PT/INR, Urinalysis OR Urine Dipstick)	X		X	X	X	X
Blood for Bone remodeling markers (P1NP, Osteocalcin, CTX)	X			X	X	X
Blood for Vitamin D testing	X					
Blood for lymphoblast culture	X			X		
Urine Pregnancy test (if applicable)	X	X				X
Blood for Genetic Testing for COL1A1 , COL1A2 , CRTAP , P3H1 , or PP1B mutations ^a	X					
Skeletal survey ^b	X					
12 Lead EKG	X		X			X
DXA Lumbar Spine ^c		X				X
DXA total hip and femoral neck ^a		X				X
Infusion of fresolimumab		X				
Pharmacokinetics		X ^e	X	X	X	X
Adverse event documentation		X	X	X	X	X

a Genetic testing will be done only if the genotype is not known

b If skeletal films are available for review to ascertain the bony deformities or scoliosis, this test will not be done

c Test may not be performed if there is significant scoliosis or the patient has had spinal instrumentation

d Test may not be done if there are pins or rods in the region of interest

e For Day 1 of the study, PK samples will be obtained prior to the infusion of fresolimumab and after the end of the infusion.

Repeat Dose Administration (Stage 2)							
Procedures	Screening	Treatment					
		1	15	30	90	180	270
	- 60 d window	±3 d window		± 14 d window			
Informed Consent	X						
Medical History	X						
Physical Examination	X		X	X	X	X	X
Vital signs - heart rate, blood pressure, respiratory rate, and body temperature	X	X	X	X	X	X	X
Height	X						X
Weight	X						X
Arm-span	X						X
Blood/urine for Safety labs (CBC, CMP, PT/INR, Urinalysis OR Urine	X		X	X	X	X	X
Blood for Vitamin D testing	X						
Bone remodeling markers (P1NP, Ocn, CTX)	X			X	X	X	X
Blood for PK ^a		X	X	X	X	X	X
Blood for lymphoblast culture	X		X	X	X		X
Blood for Antibody/Immunogenicity testing		X	X	X	X	X	X
Blood for Genetic Testing for COL1A1, COL1A2, CRTAP, P3H1,	X						
Urine Pregnancy test (if applicable)	X	X			X	X	X
Skeletal survey ^b	X						
12-lead EKG	X		X		X		X
Infusion of fresolimumab		X			X ^f	X	X ^f
DXA Lumbar Spine ^c		X					X
DXA total hip and femoral neck ^a		X					X
Peripheral quantitative CT (pQCT) of the forearm ^e		X					X
NRS		X			X	X	X
PROMIS® 29 QOL		X			X		X

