Pulmonary function test		X					X
6-minute Walk test		X					X
Adverse event documentation		X	X	X	X	X	X
Bleeding Assessment ^g			X	X			

a Genetic testing will be done only if the genotype is not known,

b If skeletal films are available for review to ascertain the bony deformities or scoliosis, this test will not be done
c this test may not be performed if there is significant scoliosis or the patient has had spinal instrumentation

d this test may not be done if there are pins or rods in the region of interest

e Will not be performed if bone deformities preclude assessment

f Will not be performed if subject is randomized into the study group to receive 2 infusions.

g Any patient who experiences clinically significant bleeding will be referred to their primary physicians or hematology specialists for appropriate work up

PK samples will be obtained prior to the infusion of fresolimumab and after the end of the infusion.

NOTE: For documentation of AE and safety, specific information regarding including history of bleeding episodes, physical examination for peripheral edema, hematomas, and gingival hyperplasia, and urinalysis OR a urine dipstick to evaluate for blood will be conducted.

5. Data and Safety Monitoring Plan

The study protocol will be reviewed and approved by the National Institutes of Health (NIH) before submission to individual center IRBs for approval. Participant enrollment may only begin with IRB approved consent forms.

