Across the clinical studies, the majority of bleeding adverse events reported have been mild, self-limited events of gum bleeding without associated gingival lesions and nose bleeding without discrete nasal lesions. Anemia was not seen with these mild, self-limited events. Patients should be carefully monitored for the development of anemia and bleeding while receiving fresolimumab.

Immune Modulation

In preclinical studies, there did not appear to be any significant immune-mediated toxicity associated with long-term neutralization of TGF β in normal mice. No evidence of significant immune dysregulation has been seen in clinical studies to date. Three patients with malignant melanoma and 1 patient with FSGS developed non-disseminated herpes zoster. The FSGS patient had a history of herpes zoster. In 1 of the 4 patients, the herpes zoster event was considered by the reporting physician to be related to therapy. It remains to be determined if fresolimumab increases the risk of herpes zoster. Patients should be carefully monitored for the development of herpes zoster. One FSGS patient developed transient vitiligo and 2 oncology patients developed hypopigmentation of skin or hair. In all 3 patients, the events were considered by the reporting physician to be treatment-related. The mechanism by which fresolimumab could be associated with vitiligo/hypopigmentation could potentially be via immune modulation however alternative non-immune mechanisms may play a role.

Reproductive Function

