5.8 Subject Discontinuation

An intent to treat approach will be used. All data acquired prior to termination for the reasons outlined below will be included in the primary analysis unless patient withdraws consent. Every effort will be made to conduct a final study visit with the participant and participants will be followed clinically until, if applicable, all adverse events resolve.

- Withdrawal of consent.
- Withdrawal by the participant.
- Withdrawal by the investigator.
- Intercurrent illness or event that precludes further visits to the study site or ability to evaluate disease (e.g.-mental status change, large pleural effusion).
- Grade 4 or higher adverse events as defined by the CTCAE or life threatening AEs not covered by the CTCAE of the same preferred term related to the study medication, excluding conditions present at baseline or those directly related to skeletal complications of Osteogenesis Imperfecta.
- Clinically significant allergy or hypersensitivity to fresolimumab.
- Pregnancy.
- QTc interval of > 500msec.
- Clinically significant oral or mucosal bleeding with resulting hemoglobin of < 8g/dL.
- Development of keratoacanthoma, squamous cell or basal cell carcinoma.
- Development of any cancer.

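### The Stage 2 Day 15 visit list omits safety labs that the schedule, as extracted, marks; Day 270 labs and observation after repeat infusions are cheap additions

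*Combined protocol and SAP*

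**What the plan says.** Section 4.8 makes laboratory variables part of the Stage 2 primary safety objective and then lists procedures visit by visit. For Day 15 the blood instruction is "Collect blood for laboratory tests (Pharmacokinetics; Immunogenicity; Lymphoblast culture". No urine sample is listed. The matching Stage 1 visit in section 4.7 reads "Collect blood for laboratory tests (Safety: CBC, CMP, PT/INR; Pharmacokinetics; Lymphoblast culture" and adds a urine sample.

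Section 4.10 has a schedule for each stage, each with a row "Blood/Urine for Safety labs (CBC, CMP, PT/INR, Urinalysis OR Urine" (apart from capitalization). In the Stage 2 table as extracted, that row carries a mark in the Day 15 position. Section 4.9 says "Data will be collected at study visits per the" Schedule of Events. A note under the Stage 2 table, tied to no particular visit, adds that "urinalysis OR a urine dipstick to evaluate for blood will be conducted".

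Group 1 receives its fourth infusion at Day 270. The blood instruction there is "Collect blood for laboratory tests (Pharmacokinetics; Bone remodeling markers", and the only urine test listed is for pregnancy. The Day 90 and Day 180 lists both include CBC, CMP and PT/INR.

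The Day 1 list sets three hours of observation after the infusion. The Day 90, 180 and 270 lists give the infusion, a PK sample afterwards and adverse event documentation, with no duration.

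**The concern.** At Day 15 the protocol gives two working instructions that disagree on a primary safety outcome. Someone preparing the visit from section 4.8 would not order the labs; someone working from section 4.10 would. The Day 15 labs are the first look at blood counts, chemistry and coagulation after the first Stage 2 dose. Section 7.5 also records procedures not done as deviations, so following the visit list faithfully would itself depart from the schedule.

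The other two items concern the repeat infusions, which are what Stage 2 adds to Stage 1. Section 5.3 says "Patients should be carefully monitored for the development of anemia and bleeding while receiving fresolimumab", yet Day 270 is the one infusion visit after Day 1 whose list has no blood count. Hypersensitivity is a ground for re-evaluating treatment (section 5.3) or stopping it (section 5.8), yet no length of observation is written for any infusion after the first.

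**Working it through.** The plan states no figure to reproduce, so the check compares text with schedule and counts days.

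**1. Is the Day 15 mark credible?** The extracted Stage 2 table has seven columns (Screening, 1, 15, 30, 90, 180, 270), but section 4.8 describes eight visits, the last at Day 360. A column has been lost at the right-hand end. At Day 15:

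| Item | Visit text | Schedule position |
|---|---|---|
| Physical examination | listed | marked |
| EKG | listed | marked |
| PK | listed | marked |
| Immunogenicity | listed | marked |
| Lymphoblast culture | listed | marked |
| Bone remodeling markers | not listed | blank |
| Safety labs | not listed | marked |

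Of these seven rows, only safety labs disagrees. After the Screening mark, the safety-lab row has one blank cell (Day 1), while the bone-marker row has two (Days 1 and 15). The Day 15 mark is therefore not a displaced Day 30 mark. Before the damaged last column the row has five marks (Screening, 15, 30, 90, 180), against four time points in the text (Screening, 30, 90, 180).

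One row counts against full trust in the table. PROMIS aligns to Day 90, whereas section 4.8 and section 4.9 put it at Day 180.

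**2. Size at Day 15.** Days from dose 1 (Day 1) to the first safety labs:
- by the schedule: 15 − 1 = 14
- by the visit text: 30 − 1 = 29
- difference: 29 − 14 = 15 days, for 8 subjects (10 with the 2 additional patients in section 6)

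**3. Day 270, conditionally.** Infusions number 4 × 4 = 16 in group 1 and 4 × 2 = 8 in group 2, 24 in all. Of these 8 are first infusions and 3 × 4 + 1 × 4 = 16 are repeats. Days to the next listed safety labs:

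| Repeat infusion | n | Visit text only | With Day 270 labs |
|---|---|---|---|
| Group 1, dose 2 (Day 90) | 4 | 180 − 90 = 90 | 90 |
| Group 1, dose 3 (Day 180) | 4 | 360 − 180 = 180 | 270 − 180 = 90 |
| Group 1, dose 4 (Day 270) | 4 | 360 − 270 = 90 | 90 |
| Group 2, dose 2 (Day 180) | 4 | 360 − 180 = 180 | 270 − 180 = 90 |

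By the text alone, 8 of 16 repeat infusions wait 180 days. If the ±14-day window applies to both end visits (an assumption), the range is 180 − 28 = 152 to 180 + 28 = 208 days. With Day 270 labs, all 16 wait 90 days. The table cannot settle which column applies. Its last column holds Day 270 content in the infusion row and Day 360 content in the DXA, pQCT and pulmonary function rows, so the last safety-lab mark could mean either visit or both.

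**4. Observation.** A duration is stated for 8 of 24 infusions and 0 of 16 repeats. Three hours after each repeat is 16 × 3 = 48 hours. With 10 subjects split 6+4, 5+5 or 4+6 between groups 1 and 2, repeats number 3 × 6 + 4 = 22, 3 × 5 + 5 = 20 or 3 × 4 + 6 = 18. That is 66, 60 or 54 hours. All counts assume no dropout.

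**The case against.** The strongest reply is that section 4.9 already settles Day 15 by pointing to the schedule, which calls for the labs. The Day 15 visit also still includes an examination, vital signs, EKG and a bleeding assessment, and the note under the table asks for a urine check for blood. All 8 planned Stage 1 subjects have Day 15 labs, and the DSMB reviews Stage 1 safety before Stage 2 begins. This limits the consequence. It does not reconcile the two instructions, and single-dose labs do not replace a primary outcome of the repeat-dose stage. The point that the mark is read from a damaged table also stands: the conflict is very likely, not certain.

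A reader might go further on four points, and the documents do not support any of them.

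- **A text/schedule contradiction at Day 270.** The last column merges two visits, so the schedule may already require these labs.
- **A hemoglobin stopping rule that cannot work without a Day 270 CBC.** The rule is "Clinically significant oral or mucosal bleeding with resulting hemoglobin of < 8g/dL". Clinical bleeding comes first and the hemoglobin follows from it. A footnote sends clinically significant bleeding for work-up, and an unscheduled count is always possible.
- **Practice varying from site to site.** Section 4.8 puts screening and Day 1 at one center and expects follow-up there, with remote or virtual visits for unforeseen or safety reasons only.
- **No observation after repeat infusions.** The lists are silent on duration only. Part of the section 5.3 risk text was not available for review, and a general rule there cannot be excluded.

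Visit spacing is not in question either. Section 4.8 justifies it by dosing that is much less frequent than in an earlier trial.

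**Conclusion.** The Day 15 point holds: the Stage 2 visit list and the schedule as extracted very probably conflict, and an omission from the list is the likeliest cause. The effect is a possible 15-day delay in the first safety labs after dose 1, for staff who follow the list. It rests on the alignment of the Day 15 column, which the neighboring rows support.

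The Day 270 labs and the observation time are worthwhile additions on visits that already exist, not demonstrated errors. The 180-day gap for 8 of 16 repeat infusions applies only if Day 270 is unmarked in the original schedule or staff follow the visit text. At Day 270 the items in doubt are CBC, CMP and PT/INR, since the note under the table already calls for urine testing.

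**What to change.** **Day 15 (reconcile).** Add CBC, CMP, PT/INR and urinalysis or dipstick to the Stage 2 Day 15 list in section 4.8 so that it agrees with section 4.10. The 8 lab sets (10 with the additional patients) are already in the schedule as extracted.

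**Day 270 (improve).** Add CBC, CMP, PT/INR and urinalysis or dipstick to the Day 270 list, using the existing blood draw, with the sample taken before the infusion in group 1. Confirm that the schedule marks this visit. This means at most 8 new sets for 8 subjects (10 with the additional patients), and none if the visit is already marked. The sponsor should state whether the result must be read before dosing.

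**Observation (improve).** Write the three-hour period into the Day 90, 180 and 270 lists for subjects infused at those visits, unless a general rule already exists. The cost is at most about 48 hours for 16 repeat infusions, or 54 to 66 hours with the 2 additional patients, and less where observation already happens.

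Otherwise the cost is protocol wording and a case report form update, with no new visits. After the change, first labs would still come about 14 days after dose 1 and about 90 days after later doses.

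### Stage 2 lists its bleeding assessment only at Days 15 and 30, so no visit after a repeat infusion lists it, in conflict with the NOTE under the schedule

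*Combined protocol and SAP*

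**What the plan says.** - **Stage 2 visit lists (section 4.8).** Day 15 has "Document adverse events include bleeding assessment". Day 30 has "Record adverse events assessment including history of any oral or mucosal bleeding". Days 90, 180, 270 and 360 call for adverse events to be documented and do not mention bleeding.
- **Stage 2 schedule (section 4.10).** The row headed "Bleeding Assessment" is marked at Days 15 and 30 and nowhere else. The row headed "Adverse event documentation" is marked from Day 1 onward.
- **NOTE under the Stage 2 schedule.** It begins "For documentation of AE and safety, specific information regarding including history of bleeding episodes, physical examination for peripheral edema, hematomas, and gingival hyperplasia" and adds a urinalysis or dipstick to look for blood. It names no visits.
- **Stage 1 visit lists (section 4.7).** Days 15 and 30 have "Record adverse events assessment including history of any oral or" mucosal bleeding. Days 90 and 180 have adverse-event recording without that prompt.
- **Section 5.3.** "Patients should be carefully monitored for the development of anemia and bleeding while receiving fresolimumab". The same paragraph says that most bleeding events seen so far were mild and self-limited.
- **Stage 2 primary objective (section 4.8).** It is the safety of repeat dosing.

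**The concern.** Bleeding is a named risk of the drug, and the events described are mostly mild. Patients may not volunteer such events unless asked. The one assessment aimed at them is listed twice in Stage 2, both times after the first infusion, although the stage exists to describe safety under repeated infusions.

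If forms are built from the row and the visit lists, bleeding would be solicited after dose 1 and left to spontaneous report after doses 2 to 4. A table of bleeding events over time could then show fewer late events because the method of asking changed. With four participants per group, a few missed mild events would alter the description.

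**Working it through.** The documents give no figure to reproduce. The check is a count of visits and infusions, followed by a comparison of the passages.

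**Infusions (section 4.8)**
- Group 1: 4 participants × 4 infusions = 16, of which 4 are first infusions and 12 are repeats.
- Group 2: 4 participants × 2 infusions = 8, of which 4 are first infusions and 4 are repeats.
- Total: 16 + 8 = 24 infusions, with 12 + 4 = 16 repeats.

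The last listed bleeding assessment is at Day 30, before any repeat infusion. The infusions with no listed bleeding assessment afterwards are therefore the repeats:
- group 1: 12/16 = 75%
- group 2: 4/8 = 50%
- overall: 16/24 = 67%

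**Visits after a repeat infusion**

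| | Repeat infusions | Later visits | Bleeding assessment listed | AE documentation listed |
|---|---|---|---|---|
| Group 1 | Days 90, 180, 270 | Days 180, 270, 360 | 0 of 3 | 3 of 3 |
| Group 2 | Day 180 | Days 270, 360 | 0 of 2 | 2 of 2 |

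Day 90 is not counted. The interval it closes follows dose 1 in both groups.

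**Recall interval.** After the first infusion the next visit is 15 − 1 = 14 days later. After any repeat infusion it is nominally 90 days later (for example 180 − 90).

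**Row and lists against the NOTE**
1. The row and the visit lists agree with each other on Days 15 and 30 only.
2. The NOTE makes bleeding history part of adverse-event documentation, which is listed at every later visit. On that reading a separate row marked at two visits is redundant. On the row's reading the NOTE does not apply in full at the other visits. The protocol does not say which reading holds.
3. The visit lists do not carry out the NOTE consistently. The Day 270 list takes urine for pregnancy testing only, with no urinalysis or dipstick, and has no CBC or PT/INR. The Stage 2 Day 15 list has no urine test, although the schedule marks safety labs there.
4. The NOTE stands under the Stage 2 table. Whether it also governs Stage 1 is not stated.

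The last column heading of the Stage 2 table is lost in the text available to me, so the Day 270 point rests on the visit list. The Day 15 and Day 30 marks are not affected.

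**Possible size (illustration only).** Suppose spontaneous report captures a fraction c of the mild bleeds that questioning would find, and a fraction f of later visits omit the questions. With a constant true rate, the apparent fall is f × (1 − c). The documents give neither value. Assuming c between 0.3 and 0.7:
- f = 1: the fall is 1 − 0.7 = 30% to 1 − 0.3 = 70%
- f = 0 (NOTE applied everywhere): the fall is 0%

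The range is 0% to 70%, and its position depends on how sites read the protocol.

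**The case against.** The strongest reply is the NOTE. It puts bleeding history, examination for hematomas and gingival hyperplasia, and a urine check into adverse-event documentation, and such documentation and a physical examination are listed at every later visit. A reader of the row alone might infer that bleeding is not asked about at all after a repeat infusion. The documents do not support that: on the NOTE's terms it is asked at 3 of 3 such visits in group 1 and 2 of 2 in group 2. Nor do they show that sites will follow the row rather than the NOTE. What stands against this reply is that the row and the visit lists say something different, and that the Day 270 list omits the urine check.

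Four further objections carry weight.
- **No planned contrast by dose number.** Section 6 summarises adverse events descriptively by dose group. Any bias would sit in that description and in how its timing is read, not in a test.
- **Both groups share one calendar of assessments.** This is true. The uncovered share of infusions still differs, 75% against 50%, because group 1 has more repeats.
- **The bleeding criterion in section 5.8.** A reader might infer that it would go undetected. It also requires a hemoglobin below 8 g/dL, and CBC is listed at Days 180 and 360 whatever the row says. The mild events in section 5.3 occurred without anemia.
- **Section 5.3 sets no visits.** Its request for monitoring is general and can be met in several ways. Part of that section was not available to me and may say more about bleeding.

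**Conclusion.** The point holds as an internal conflict with a possible effect on safety ascertainment. The dedicated assessment is listed at no visit after a repeat infusion, and 16 of 24 planned infusions have none listed afterwards. The NOTE points the other way without naming visits. Stage 1 visit text shows the same two-visit pattern, but with a single infusion the repeat-dose argument does not apply there.

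The bias towards fewer late bleeds is conditional on sites or forms following the row and visit lists. Its size is unknown. A definite fall of 30% to 70% cannot be claimed, since it rests on an assumed capture rate and on the NOTE being ignored at every later visit; near zero is equally consistent with the documents.

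The counts assume the planned eight Stage 2 participants. The two optional extra participants would change the totals but not the share within each group (3 of 4 infusions per participant in group 1, 1 of 2 in group 2). The change is worth making because bleeding is a named risk, repeat-dose safety is the primary objective, and the edit costs almost nothing.

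**What to change.** - Mark the bleeding assessment at every post-dose visit: add Days 90 and 180 in Stage 1, and Days 90, 180, 270 and 360 in Stage 2. Use identical questions each time and a recall period running from the last visit.
- Reword the row, the visit lists and the NOTE so that they agree, and state which stages and visits the NOTE covers.
- Reconcile the Day 270 list with the NOTE's urine check, and the Stage 2 Day 15 list with the schedule and the NOTE.
- Build the case report form from the reconciled text.

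The cost is a few questions at visits already held, plus edits to the schedule and visit text. If reconciliation confirms the urine check, there is also a dipstick or urinalysis where the list now has none. Even prompting does not shorten the roughly 90-day recall after a repeat infusion, so the safety report should state that limitation.
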